3.3 Exploratory Objectives

- a. To evaluate rates of PD-L1 positive expression (by CPS score ≥ 1 and ≥ 10), MSI status, TMB and EBV status in pre-treatment biopsy specimens.
- b. To evaluate whether PD-L1 expression, MSI status, TMB and/or EBV status in pre-treatment biopsy specimen is a predictive biomarker for pCR/PRG/R0 to pembrolizumab and other clinical outcomes.
- c. To evaluate interval change in PD-L1 expression (by CPS score) pre/post pembrolizumab therapy in resected pathological specimens (if residual tumor is present).
- d. To determine the somatic genomic changes of actionable cancer related genes (mutation, amplification, indels, and translocation) using targeted deep next-generation sequencing (NGS) oncopanel in pre-treatment specimen and in resected specimen (if tumor is still present) and correlate with clinical outcomes (pCR/PRG, R0 rate, DFS, OS) and other molecular markers.
- e. To evaluate ctDNA NGS pre-pembrolizumab, post-pembrolizumab, post-surgery, and if applicable at time of recurrence, and correlate with clinical outcomes (pCR/PRG, R0 rate, DFS, OS) and molecular markers.
- f. To determine baseline and interval changes in whole-exome RNAseq expression analysis pre-/post- therapy.
- g. To evaluate fecal flora via Fecal 16S RNA seq pre-pembrolizumab, post-pembrolizumab, post-surgery, and if applicable at time of recurrence, and correlate with clinical outcomes.

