2.2 Trial Diagram

3.0 OBJECTIVES & HYPOTHESES

3.1 Primary Objective & Hypothesis

Objective:

To determine the pathologic complete response (pCR) rate in patients with cT1b-T2N0 GEA treated with neoadjuvant pembrolizumab followed by surgical resection.

Regression of the primary tumor will be documented by the amount of viable tumor versus the amount of fibrosis (Becker Criteria), ranging from no evidence of any treatment effect to a complete response with no viable tumor identified, as previously described[1] [Grade 1a: complete remission (pCR), no residual tumor/tumor bed; Grade 1b: subtotal remission, <10% residual tumor/tumor bed; Grade 2: partial remission, 10-50% residual tumor/tumor bed; Grade 3: minor/no remission, >50% residual tumor/tumor bed].

Hypothesis:

The pCR rate (Grade 1a+b response) in patients with cT1b-T2N0 GEA who receive neoadjuvant pembrolizumab followed by surgical resection will be 15%, whereas historical patients treated with surgery alone have a pCR rate of virtually 0%. [2, 3]

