The [name] lab has previously demonstrated a correlation between fecal flora composition and response to immunotherapeutics.[39, 40] In this trial, patient fecal microbiomes will be characterized before pembrolizumab therapy, after pembrolizumab therapy, after surgery, and at time of recurrence (if applicable) in order to evaluate the relationship between fecal flora and therapeutic response.

Patients who do not respond to immunotherapy may have various mechanisms of primary and/or acquired resistance. Genomic alterations will be characterized using targeted NGS in the pre-treatment specimen as well as in the resected specimen (if residual tumor is present) to evaluate if non-responders have particular mechanisms of resistance to therapy. Additional ctDNA will be evaluated before pembrolizumab therapy, after pembrolizumab therapy, after surgery, and at time of recurrence (if applicable) to characterize genomic alterations at diagnosis, identify temporal trends, identify ctDNA alterations that may be predictive of outcomes, and determine if presence of residual tumor ctDNA post-operatively is predictive of outcomes.

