8.1.2.6 Tumor Tissue Collection and Correlative Studies Sampling

Patients will undergo tumor and blood collection as per routine clinical practice and will be consented to IRB 16294A prospective protocol for all indicated correlatives.

Tissue specimens collected at diagnosis and at time of surgical resection will be obtained per standard-of-care (SOC) practices. As per SOC at this institution, tissue at diagnosis and/or at time of surgical resection (if tumor is still present) will undergo testing for MSI via immunohistochemistry (IHC), HER2 testing (via IHC and/or fluorescence in situ hybridization (FISH)), and Epstein-Barr encoding region in situ hybridization (EBER ISH). These specimens will also undergo PD-L1 CPS testing, whole-exome RNAseq expression, as well as NGS testing via Foundation One CDx™ (Foundation Medicine, Cambridge, MA). ctDNA using Guardant360 (Guardant Health, Redwood, CA) will be evaluated before pembrolizumab therapy, after pembrolizumab therapy, after surgery, and at time of recurrence (if applicable) as per SOC.

Finally, patient fecal microbiomes will be characterized using fecal 16S RNA sequencing before pembrolizumab therapy, after pembrolizumab therapy, after surgery, and at time of recurrence (if applicable) as discussed below.

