9.0 STATISTICAL ANALYSIS PLAN

9.1 Statistical Analysis Plan Summary

9.2 Statistical Analysis Plan

At our institution, patients with cT1b-2N0M0 GEA typically undergo surgery alone without additional therapy. Thus, we expect 100% of resected specimens to have evidence of cancer in historical controls. We hypothesize that neoadjuvant pembrolizumab will result in a pCR rate (Grade 1a+1b) of 15%. A sample size of 33 patients will provide 90% power with one-sided alpha 0.1 to detect this pCR rate using neoadjuvant pembrolizumab. More specifically, we will use an optimal, Simon two-stage design to test the null hypothesis that the Grade 1 response rate is 1% vs. the alternative that it is 15%. Fifteen patients will be enrolled in the first stage and if no complete pathological responses are observed the trial will be terminated for futility. If one or more responses are seen, an additional 18 patients will be studied for a total of 33. Two or more responses in 33 patients will indicate that the treatment is promising, whereas 0/15 or 1/33 will be considered a negative result. Patients who receive pembrolizumab but do not go to surgery will be counted as not having achieved a pCR.

We will also assess activity in the subset of patients who are PD-L1 positive. Assuming an approximate PD-L1 positivity incidence (CPS score ≥ 1) of 50% of all patients enrolled, this sample size of 16 expected PD-L1 positive patients will provide over 95% power with one-sided alpha 0.05 to detect a pCR rate (Grade 1a+1b) of 30% vs. 1% using neoadjuvant pembrolizumab in this preplanned subset. Using a higher CPS cutoff of ≥ 10 we assume 20% of patients will be PD-L1 positive based on recent data, and the sample size of 7 expected PD-

L1 positive patients will provide 67% power with one-sided alpha 0.05 to detect a pCR rate (Grade 1a+1b) of 30% vs. 1%

Complete responses (R0) will be tabulated along with an exact 90% confidence interval. DFS and OS will be estimated using the Kaplan-Meier method. Adverse events will be summarized by type, grade, and attribution to the study drug.

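### Objective 3.3d correlates resected-specimen sequencing with pCR, but a Grade 1a patient can never have a resected-specimen result

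*Combined protocol and SAP*

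**What the plan says.** Objective 3.3d in Section 3.3 applies targeted sequencing to two specimens and relates both to the same outcomes: "in pre-treatment specimen and in resected specimen (if tumor is still present) and correlate with clinical outcomes (pCR/PRG, R0 rate, DFS, OS". Section 4.2.3.2 names the tissue to be sequenced and the purpose: "pre-treatment specimen as well as in the resected specimen (if residual tumor is present) to evaluate if non-responders have particular mechanisms of resistance to therapy".

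Footnote d of the Section 7.1 flow chart and Section 8.1.2.6 repeat that resected tissue is tested only when tumor remains.

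Section 3.1 defines the grades that matter here: "Grade 1a: complete remission (pCR), no residual tumor/tumor bed" and "Grade 1b: subtotal remission, <10% residual tumor/tumor bed". It uses pCR in two senses: as the label for Grade 1a in that list, and as Grade 1a plus 1b in the hypothesis. Section 9.2 tests the second. Section 6.6 scores a treated patient who does not reach surgery as Grade 3.

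For analysis, Section 9.2 names responder versus non-responder comparisons of pre-treatment PD-L1 and other markers, and paired tests for change. It has no rule for patients without a resected-tumor result.

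**The concern.** Whether a resected-specimen value exists depends on the outcome it is to be correlated with. The best responders have no tumor left to sequence. Any responder who is sequenced is Grade 1b, selected for incomplete clearance, and need not resemble Grade 1a biologically. Missingness also arises at the other end, because patients scored Grade 3 for lack of surgery have no specimen.

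The main harm is selection, which a larger sample would not remove. A marker that looks different between response groups in resected tissue may reflect who still had tumor rather than who responded. The second harm is that the responder group, already small, becomes smaller. Section 4.2.1 presents the pre- and post-treatment tissue as a purpose of the study, so these results are likely to be reported.

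**Working it through.** **The plan's own figures.** Inputs from Section 9.2: 15 patients in stage 1, stop if no response; 33 in total, success with 2 or more; rates 1% and 15%. The probability of success at rate p is

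1 − (1−p)^15 − 15p(1−p)^14 × (1−p)^18.

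- p = 0.15: 1 − 0.0874 − 0.0124 = 0.900, matching the stated 90% power.
- p = 0.01: 1 − 0.8601 − 0.1087 = 0.031, inside the one-sided 0.10 limit.

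The design reproduces. The plan states no sample size or power for the resected-specimen correlation.

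**Assayable responders.** Expected responders (Grade 1a plus 1b) are 33 × 0.15 = 4.95, leaving 28.05 in Grades 2 and 3. Let f be the share of responders who are Grade 1a. The documents do not give f, so it is varied over its whole range. Then:

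- assayable responders = 4.95(1−f);
- response rate among assayable patients = 4.95(1−f) / (33 − 4.95f);
- chance of fewer than two assayable responders = (1−q)^33 + 33q(1−q)^32, with q = 0.15(1−f).

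| f (assumed) | Assayable responders | Rate among assayable | Chance of fewer than 2 |
|---|---|---|---|
| 0% | 4.95 | 15.0% | 3% |
| 25% | 3.71 | 11.7% | 10% |
| 50% | 2.48 | 8.1% | 28% |
| 75% | 1.24 | 4.2% | 65% |
| 100% | 0 | 0% | 100% |

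At f = 50%, for example: 2.475 / 30.525 = 8.1%, and 0.076 + 0.204 = 0.281.

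If pCR means Grade 1a alone, no pCR patient is assayable at any f above zero and the correlation is undefined.

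The table assumes that 33 patients are treated, ignores stopping after stage 1, and takes every Grade 1b, 2 and 3 patient to have a usable specimen. Patients without surgery would reduce the assayable non-responders and so raise the rate in the third column somewhat. They would not change the number of assayable responders.

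**Illustration of the loss of numbers.** Exact Fisher power, two-sided 0.05, against 28 non-responders. The marker frequencies are assumptions (responders versus non-responders).

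| Assayable responders | 80% vs 20% | 10% vs 60% |
|---|---|---|
| 5 | 73% | 53% |
| 4 | 61.5% | 36.5% |
| 3 | 51.5% | 19% |
| 2 | 32% | 1% |
| 1 | 0.2% | 0% |

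The second contrast has the direction expected of a resistance marker. Neither column includes the selection effect.

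**The case against.** The strongest reply is that the limit is disclosed wherever resected tissue is mentioned, the objective is exploratory, and changes acquired under treatment can be seen only in residual tumor set against the patient's own baseline. All of that stands. It supports keeping the resected specimen for paired change. It does not support the correlation with pCR, which 3.3d keeps in the same sentence as the disclosure.

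A fair further point is that regression grade is an ordered outcome, so a description across Grades 1b, 2 and 3 has some value. That also stands, and the fix leaves room for it.

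Three stronger readings are tempting, and the documents do not support them.

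- *The whole resistance question is conditioned on its outcome.* Section 4.2.3.2 and objective 3.3d also use the pre-treatment specimen, which is available whatever the response, and ctDNA under 3.3e does not depend on residual tumor in the specimen. Only the resected half is affected.
- *The PD-L1 subset is contaminated.* Section 9.2 says "We will also assess activity in the subset of patients who are PD-L1 positive" and names no specimen there. But 3.3a sets PD-L1 positivity at the same CPS cutoffs in pre-treatment biopsies, 3.3b uses that biopsy for PD-L1, MSI, TMB and EBV as predictors of response, and 3.3c gives resected PD-L1 only a role in measuring change.
- *Patients with residual tumor get two chances to test positive.* Section 8.1.2.6 says "tissue at diagnosis and/or at time of surgical resection (if tumor is still present) will undergo testing". That describes which tissue is tested. It is not a rule for assigning marker status, and nothing in the documents pools the two specimens. The flow chart lists them as separate rows.

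**Conclusion.** The point holds for one part of one exploratory objective. The resected-specimen comparison with pCR and regression grade in 3.3d is conditioned on the outcome, and Section 9.2 has no rule for it. The comparison is empty if pCR is Grade 1a. Under the working definition of Grade 1a plus 1b it is not empty, but it is depleted and selected. At the planned response rate, the chance of fewer than two assayable responders runs from 3% to 65% as the Grade 1a share goes from 0 to 75%.

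The structural conclusion follows from the protocol's definitions alone. Its size rests on the assumed Grade 1a share, and the power figures also rest on assumed marker frequencies.

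Severity is low. The primary test, the sample size of 33, the stage 1 rule and the PD-L1 subset power are not affected.

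**What to change.** In 3.3d and Section 4.2.3.2, base the association of genomic alterations with pCR and regression grade on the pre-treatment specimen, as 3.3b already does for PD-L1, MSI, TMB and EBV. Assign resected-specimen sequencing two uses: paired pre/post change within patients, and descriptive results across Grades 1b to 3. Label both as conditional on residual tumor.

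Report the number of patients without a resected result by grade, and separate Grade 3 patients who had no surgery from those with a specimen. Section 9.2 could repeat that PD-L1 status is pre-treatment, but this is optional.

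The cost is wording only, since the flow chart already schedules the pre-treatment biopsy. What is given up is the resected-specimen versus pCR comparison, which cannot answer its question.

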4.0 BACKGROUND & RATIONALE

4.1 Background

Pembrolizumab is a potent humanized immunoglobulin G4 (IgG4) monoclonal antibody (mAb) with high specificity of binding to the programmed cell death 1 (PD-1) receptor, thus inhibiting its interaction with programmed cell death ligand 1 (PD-L1) and programmed cell death ligand 2 (PD-L2). Based on preclinical in vitro data, pembrolizumab has high affinity and potent receptor blocking activity for PD-1. Pembrolizumab has an acceptable preclinical safety profile and is in clinical development as an intravenous (IV) immunotherapy for advanced malignancies. Keytruda® (pembrolizumab) is indicated for the treatment of patients across a number of

indications because of its mechanism of action to bind the PD-1 receptor on the T cell. For more details on specific indications refer to the Investigator brochure.

Pembrolizumab is FDA approved for third line treatment of recurrent locally advanced or metastatic CPS ≥ 1 PD-L1+ GEA [4, 5] and for second line treatment of unresectable or metastatic microsatellite high (MSI-H) or mismatch repair deficient (dMMR) GEA. [5, 6] As the role of pembrolizumab continues to be investigated in the metastatic setting, newer trials are investigating the use of checkpoint blockade in the perioperative setting. KEYNOTE-585 is examining whether the addition of pembrolizumab to chemotherapy improves outcomes in the neoadjuvant or adjuvant setting in untreated patients with cT3 or cN+ GEA (NCT03221426). [7] CheckMate 577 is enrolling patients with stage II or III carcinoma of the esophagus of EGD (squamous cell carcinoma and AC) treated with chemoradiation followed by surgery, who have an R0 resection yet residual disease, to receive nivolumab or placebo adjuvantly (NCT02743494). [8]

4.1.1 Pharmaceutical and Therapeutic Background

The importance of intact immune surveillance function in controlling outgrowth of neoplastic transformations has been known for decades. [9] Accumulating evidence shows a correlation between tumor-infiltrating lymphocytes in cancer tissue and favorable prognosis in various malignancies. In particular, the presence of CD8+ T-cells and the ratio of CD8+ effector T-cells/FoxP3+ regulatory T-cells (T-reg) correlates with improved prognosis and long-term survival in solid malignancies, such as ovarian, colorectal, and pancreatic cancer; hepatocellular carcinoma; malignant melanoma; and renal cell carcinoma. Tumor-infiltrating lymphocytes can be expanded ex vivo and reinfused, inducing durable objective tumor responses in cancers such as melanoma. [10, 11]

The PD-1 receptor-ligand interaction is a major pathway hijacked by tumors to suppress immune control. The normal function of PD-1, expressed on the cell surface of activated T-cells under healthy conditions, is to down-modulate unwanted or excessive immune responses, including autoimmune reactions. PD-1 (encoded by the gene *Pdcd1*) is an immunoglobulin (Ig) superfamily member related to cluster of differentiation 28 (CD28) and cytotoxic T-lymphocyte-associated protein 4 (CTLA-4) that has been shown to negatively regulate antigen receptor signaling upon engagement of its ligands (PD-L1 and/or PD-L2). [12, 13]

The structure of murine PD-1 has been resolved. [14] PD-1 and its family members are type I transmembrane glycoproteins containing an Ig-variable-type (IgV-type) domain responsible for ligand binding and a cytoplasmic tail responsible for the binding of signaling molecules. The cytoplasmic tail of PD-1 contains 2 tyrosine-based signaling motifs, an immunoreceptor tyrosine-based inhibition motif, and an immunoreceptor tyrosine-based switch motif. Following T-cell stimulation, PD-1 recruits the tyrosine phosphatases, SHP-1 and SHP-2, to the immunoreceptor tyrosine-based switch motif within its cytoplasmic tail, leading to the dephosphorylation of effector molecules such as CD3 zeta (CD3 ζ), protein kinase C-theta (PKC θ), and zeta-chain-associated protein kinase (ZAP70), which are involved in the CD3 T-cell signaling cascade. [13, 15-17] The mechanism by which PD-1 down-modulates T-cell responses is similar to, but distinct from, that of CTLA-4, because both molecules regulate an overlapping

set of signaling proteins. [18, 19] As a consequence, the PD-1/PD-L1 pathway is an attractive target for therapeutic intervention in gastroesophageal adenocarcinoma.

4.1.2 Preclinical and Clinical Trial Data

Refer to the Investigator's Brochure for Preclinical and Clinical data.

4.2 Rationale

4.2.1 Rationale for the Trial and Selected Population

Gastroesophageal cancer is the second leading cause of cancer mortality worldwide. [20] Surgery and endoscopic resection are the only curative options for patients with early stage and/or locally advanced operable GEA. Survival is highly dependent on the extent of disease at presentation, in particular the depth of invasion and nodal status, as well as ability to obtain a complete (R0) resection and pCR. [21] The role of perioperative chemotherapy is clear in \geq cT3 and/or \geq cN1 disease where R0 resection rates are 80-90% and pCR 15-25%. However, the benefit of such therapy in cT2N0 disease is less certain, and in cT1bN0 disease even less well studied. This is in part due to significant heterogeneity that exists in the enrollment criteria for the major clinical trials that have guided the use of neoadjuvant therapy. Trials have varied in their inclusion of cT2N0 disease, use of EUS for staging, use of AJCC staging system, and reporting of outcomes by T and N status. There is thus great heterogeneity across treatment centers regarding the inclusion of cT1b-2N0 patients in perioperative therapy approaches. A recent retrospective analysis of 1704 patients with cT2N0 gastric cancer found that there was no overall survival benefit derived from neoadjuvant and/or perioperative chemotherapy compared to surgery alone.[22]

However, patients with cT2N0 esophageal adenocarcinoma (AC) (clinical stage IIB based on the AJCC 8th edition) have a 5-year risk-adjusted survival of only ~42% [23], a dismal number, and actually comparable to patients with stage III colon cancer where routine adjuvant therapy is implemented. Patients with cT1N0 esophageal AC (clinical stage I), have a 5-year risk-adjusted survival of only approximately 68%. Patients with cT1-2N0M0 gastric AC (clinical stage I) have an estimated 5-year survival of 57%. [24] There is a clear need to improve on outcomes in patients with operable GEA. It is quite evident that the optimal treatment of cT1-2N0 GEA is controversial without widespread implementation of any perioperative therapy, yet with acknowledged relatively poor outcomes. At the University of Chicago and many other centers, the standard of care for cT1-2N0 GEA is surgical or (endoscopic mucosal resection/dissection if early stage I cT1a) followed by observation.

Recently, immune checkpoint blockade has emerged as a promising therapeutic strategy in GEA as discussed above. An unexplored area of research is whether neoadjuvant checkpoint blockade can improve outcomes in patients with cT1-2N0 GEA. In KEYNOTE-012, a phase 1b trial of pembrolizumab in recurrent or metastatic PD-L1+ GEA, the median time to response was 8 weeks.[25] This median time to response has been now observed in other follow up studies of checkpoint inhibition in this disease. Thus, in cT1b-2N0 patients who would ordinarily undergo surgery alone, neoadjuvant pembrolizumab could, in a short amount of time, induce a response and still allow for surgery to be performed in a timely manner. Furthermore, the proportion of

MSI-H tumors (which are more sensitive to PD-1 blockade) appears to be enriched in the early stage setting compared to the metastatic setting in which pembrolizumab is currently approved. Moreover, the rate of PD-L1 positivity has been reported to be generally higher in earlier stage disease. Thus, these early stage patients, who otherwise have a moderate chance of recurrence with surgery alone, may in particular be worth targeting with neoadjuvant pembrolizumab.

A potential concern may be that neoadjuvant pembrolizumab could delay curative surgery, allowing an early stage GEA to progress. However, a non-concurrent long term follow up study of patients with early gastric cancer elucidated the natural history of this disease and found that the median duration of those remaining in the early stage was 44 months. [26] Thus it is unlikely that delaying surgery by 8-11 weeks in order to obtain 3 doses of pembrolizumab would result in a clinically meaningful progression. Furthermore, in practice, surgery is often not scheduled for approximately 2-6 weeks after staging is complete, so the incremental delay attributed to receiving pembrolizumab is likely even less. Finally a recent neoadjuvant study in lung cancer demonstrated feasibility and safety in a similar setting.[27] This pilot study will provide early efficacy of pembrolizumab monotherapy using a pCR surrogate endpoint, and will also lend important pre- and post-pembrolizumab tissue for biomarkers analyses.

